5.4.3 Subgroup Analysis

The treatment effect in subjects based on baseline factors will be assessed in exploratory analyses. Analyses of subgroups will be considered exploratory and used to suggest hypotheses for further investigation in future studies.

The subgroups of interest include the following: amblyopic-eye visual acuity, age (in younger cohort only), the presence of a tropia, and prior amblyopia treatment.

In accordance with NIH guidelines, a subgroup analysis of treatment effect according to gender, as well as race/ethnicity, will be conducted. However, based on results from previous ATS studies, a differential treatment effect by these variables is not expected.

The general approach for these exploratory analyses will be to conduct an analysis of covariance similar to the primary analysis including an interaction for treatment and the subgroup covariate of interest. If the overall F-test for interaction is not statistically significant ($p > 0.05$), then no subgroup comparisons will be computed, but this will not be interpreted as conclusive evidence of no subgroup effect given that power for the tests of interaction is low.

The subgroup definitions for the planned subgroup analyses are as follows:

1. Amblyopic-eye visual acuity at baseline (20/40, 20/50, 20/63, 20/80 or worse)
2. Presence of a heterotropia at baseline (yes/no)
3. Age (years) at baseline (5 to <7, 7 to <13)
4. Prior amblyopia treatment (yes/no)

5.4.4 Treatment Compliance (Binocular computer treatment group)

Compliance will be evaluated for each treatment group based on both the parent-completed compliance calendars and automated iPad program logs. For the latter, the distribution of the total time spent playing the iPad program will be calculated based on the program logs. Both total play time since baseline and total play time since the previous visit will be computed. Compliance will be assessed at 4, 8, 12, and 16 weeks and the relationship between visual acuity improvement and total play time will be evaluated at 16 weeks.

5.4.5 Stereoacuity

Change in stereoacuity from baseline to 16 weeks will be tabulated for each group and compared between treatment groups using the exact Wilcoxon rank-sum test.

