2.4 Procedures at the Enrollment Visit

All examination procedures must be tested within 7 days prior to the date of enrollment, except the cycloplegic refraction and ocular examination, which may be performed within 7 months prior to enrollment. All examination procedures at enrollment are performed in the subject's current correction, if required (testing in trial frames is not permitted), and without cycloplegia:

1. Distance Visual Acuity Testing: Monocular distance visual acuity testing will be performed in current refractive correction (if required) in each eye by a certified examiner using the electronic ATS-HOTV visual acuity protocol for children <7 years and the E-ETDRS visual acuity protocol for children ≥ 7 years on a study-certified acuity tester displaying single surrounded optotypes as described in the *ATS Testing Procedures Manual*.
 - Testing must be completed without cycloplegia and with spectacles or contact lenses, if worn (trial frames not allowed at enrollment)
 - The same visual acuity protocol will be used throughout the study regardless of age at follow-up.
2. Stereoacuity Testing:
 - Stereoacuity will be tested at near in current refractive correction using the Randot Butterfly and Randot Preschool stereoacuity tests.
3. Ocular Alignment Testing:
 - Ocular alignment will be assessed in current refractive correction by the cover/uncover test, simultaneous prism and cover test (SPCT), and prism and alternate cover test (PACT) in primary gaze at distance (3 meters) and at near (1/3 meter) as outlined in the *ATS Procedures Manual*.
 - See *section 2.2.1* for eligibility criteria related to ocular alignment.
4. Additional Clinical Testing:
 - Ocular examination as per investigator's clinical routine (if not performed within 7 months)
5. Nonius Cross Alignment
 - Subjects will be tested to see if they are able to align the nonius cross presented on the iPad. Subjects unable to fuse the cross are not eligible for the study.
6. Demonstration of Game Understanding
 - Subjects must demonstrate that they understand the game by scoring at least one completed line while playing the game set to the easy level in the office. Subjects unable to score a line are not eligible for the study.

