3.5 Follow-up Visit Testing Procedures

Subjects will be seen at follow-up visits as outlined in *section 3.4*. A Masked Examiner must complete distance visual acuity and stereoacuity testing at these visits (*section 3.5.1*). All procedures will be performed with the subject's current refractive correction. If a subject currently wears spectacles but is not wearing them at the follow-up examination for whatever reason, testing must be performed in trial frames.

Prior to the Masked Examiner entering the room, subjects and parents should be instructed not to discuss their treatment with the Masked Examiner.

The following procedures should be performed at each visit:

1. Diplopia Questionnaire

- The child and parent(s) will be specifically questioned regarding the presence and frequency of any diplopia since the last study visit using a standardized diplopia assessment (*see ATS Miscellaneous Testing Procedures Manual*). The diplopia assessment must be performed prior to any other testing during the exam.

2. Distance Visual Acuity Testing (masked):

- Monocular distance visual acuity testing will be performed in habitual refractive correction in each eye using the same visual acuity testing method that was used at enrollment, as described in the *ATS Testing Procedures Manual*.
 - Testing must be completed without cycloplegia.

3. Stereoacuity Testing (masked):

- Stereoacuity will be tested in habitual current refractive correction using the Randot Butterfly test and Randot Preschool Stereoacuity test at near (1/3 meter).

4. Ocular Alignment Testing:

- Ocular alignment will be assessed in habitual refractive correction by the cover/uncover test, simultaneous prism and cover test (SPCT), and prism and alternate cover test

(PACT) in primary gaze at distance (3 meters) and at near (1/3 meter) as outlined in the *ATS Procedures Manual*.

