5.3 Primary Analysis

Two treatment approaches will be evaluated within each of the age cohorts as follows:

1. Binocular treatment: Binocular computer game play 1 hour per day, 7 days per week (minimum of 4 days per week)
2. Patching treatment: Patching 2 hours per day, 7 days per week

An analysis of covariance (ANCOVA) will be performed to compute the 16-week mean change in visual acuity for each treatment group, adjusted for baseline acuity and baseline age, and a 95% confidence interval will be constructed on the treatment group difference. Linearity assumptions will be evaluated for baseline visual acuity and baseline age and these factors will be treated as continuous covariates if the model assumptions are met.

For the younger age cohort (5 to <13 years of age), the upper limit of a 1-sided 95% confidence interval on the treatment effect (Patching – Binocular treatment) will be compared with the non-

inferiority limit of 0.05 logMAR. Non-inferiority of binocular treatment will be declared if the upper 1-sided confidence interval limit is less than the non-inferiority margin of 0.05 logMAR. In the event that non-inferiority of binocular treatment is declared, a test for superiority of binocular treatment will be performed using the same 95% confidence interval and pre-specified margin.

For the older age cohort (13 to <17 years of age), superiority of binocular treatment will be declared if the treatment effect (Binocular treatment – Patching) is positive and the 95% confidence interval on the treatment group difference in mean visual acuity change excludes zero.

The primary analysis will follow the intent-to-treat principle. Data will be included only from subjects who complete the 16-week exam within the predefined analysis window. There will be no imputation of data for subjects who are lost to follow-up or withdraw from the study prior to the 16-week exam. In a secondary approach to the primary analysis, multiple imputation for missing data will be performed and results of the analysis with imputation of missing data assessed for consistency with the primary analysis. A separate analysis also will be conducted including only subjects whose outcome exams were performed within the protocol time window for the visit.

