5.4 Secondary Analyses

Secondary analyses will be conducted separately for both the primary and the secondary study cohorts. All treatment group comparisons will consist of a test of the usual null hypothesis of no difference between groups; the non-inferiority hypothesis will not be tested in secondary analyses for the younger cohort.

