5.4.7 Safety

5.4.7.1 Visual Acuity in Fellow Eye

The mean change in fellow-eye visual acuity from baseline to 16 weeks will be calculated and compared between treatment groups using ANCOVA with adjustment for baseline visual acuity. The proportion of subjects with loss of 2 or more logMAR lines (10 or more letters) of visual acuity in the fellow eye from baseline to the 16-week exam will be reported for each treatment group and compared using the Fisher exact test.

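### Stereoacuity change is compared with a valid but unadjusted rank-sum test; using baseline stereoacuity as a covariate or stratum would usually gain power at little cost

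*Protocol*

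**What the plan says.** Section 5.4.5 is a single sentence. It has the change over the 16 weeks tabulated by arm and "compared between treatment groups using the exact Wilcoxon rank-sum test". It names no covariate and no stratification factor.

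Baseline stereoacuity is available. Section 2.4 lists it among the enrollment procedures: "Stereoacuity will be tested at near in current refractive correction using the Randot Butterfly and Randot Preschool stereoacuity tests". Section 3.5 repeats the same two tests at every follow-up visit, performed by a masked examiner.

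The comparison is secondary and is made separately in each cohort. Under Section 5.4, "All treatment group comparisons will consist of a test of the usual null hypothesis of no difference between groups". The protocol states no power, effect size or sample size for stereoacuity.

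The main visual acuity analyses in the same chapter do adjust. The primary ANCOVA in Section 5.3 is "adjusted for baseline acuity and baseline age". The binary acuity outcomes (5.4.1) and the time-course model (5.4.2) adjust for baseline acuity, and mean fellow-eye change (5.4.7.1) is "compared between treatment groups using ANCOVA with adjustment for baseline visual acuity".

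**The concern.** The trial tests a binocular treatment, and the background in Section 1.1 cites stereoacuity gains in the earlier studies. Stereoacuity is therefore one of the more informative secondary outcomes, and it is worth analysing efficiently.

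Subtracting baseline does not remove its influence. If the scale has a lowest level (no measurable stereoacuity) and a best level, a child at the bottom can only stay or improve, and a child at the top can only stay or worsen. Change scores then remain correlated with the starting level, and that variation goes into the comparison as noise.

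The design does not balance baseline stereoacuity directly. Section 2.5 stratifies by site and age subgroup in the younger cohort and by site and amblyopic-eye acuity in the older cohort, and deliberately not by presence of a tropia. Adjustment in the analysis is the remaining way to use the baseline measurement. What is at stake is the precision of one secondary comparison per cohort.

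**Working it through.** **Cohort sizes (protocol figures, reproduced first).** The protocol gives no figure for stereoacuity, so the evaluable sizes for the primary analysis are used.
- Younger cohort (5.2.1): SD 0.15 logMAR, margin 0.05, one-sided alpha 0.05, power 90%. n per group = 2 × (1.645 + 1.282)² × (0.15/0.05)² ≈ 154.2, so 155 per group and 310 in total, as stated.
- Older cohort (5.2.2): SD 9 letters, difference 5, two-sided alpha 0.05, power 90%. n per group = 2 × (1.960 + 1.282)² × (9/5)² ≈ 68.1, so 69 per group (138) by the normal approximation. The noncentral t distribution gives 70 per group (140), as stated.

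**Guide on a continuous scale.** With equal variance σ² at both times and correlation ρ, the change score has variance 2σ²(1 − ρ) and the ANCOVA residual has variance σ²(1 − ρ²). The ratio is (1 − ρ²) / [2(1 − ρ)] = (1 + ρ)/2: 0.75 at ρ = 0.5, 0.85 at 0.7 and 0.95 at 0.9. Adjustment helps most when the correlation is moderate.

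**Simulation on an ordinal scale.** The protocol does not give the scale, the baseline distribution or the correlation, so these are assumptions:
- a latent bivariate normal cut into 7 ordered levels, with the lowest (nil) holding 20% or 50% of children at baseline and the rest in equal shares;
- ρ of 0.5, 0.7 or 0.85;
- a latent treatment shift of 0.25 SD at 155 per group or 0.37 SD at 70 per group;
- two-sided alpha 0.05 and 1,500 simulated trials per setting.

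Three analyses were compared: rank-sum on change (large-sample version, standing in for the exact test), rank ANCOVA (ranks of the 16-week level regressed on ranks of baseline, residuals compared between arms), and a rank-sum test stratified by baseline level (van Elteren).

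| Per group | Nil share | ρ | Rank-sum on change | Rank ANCOVA | Stratified rank-sum | Gain, rank ANCOVA (points) |
|---|---|---|---|---|---|---|
| 155 | 20% | 0.5 | 0.517 | 0.661 | 0.649 | 14.4 |
| 155 | 20% | 0.7 | 0.711 | 0.805 | 0.794 | 9.5 |
| 155 | 20% | 0.85 | 0.917 | 0.950 | 0.951 | 3.3 |
| 155 | 50% | 0.5 | 0.451 | 0.579 | 0.576 | 12.8 |
| 155 | 50% | 0.7 | 0.629 | 0.710 | 0.705 | 8.1 |
| 155 | 50% | 0.85 | 0.858 | 0.885 | 0.880 | 2.7 |
| 70 | 20% | 0.5 | 0.503 | 0.636 | 0.613 | 13.3 |
| 70 | 20% | 0.7 | 0.692 | 0.781 | 0.761 | 8.9 |
| 70 | 20% | 0.85 | 0.902 | 0.946 | 0.928 | 4.4 |
| 70 | 50% | 0.5 | 0.469 | 0.589 | 0.577 | 11.9 |
| 70 | 50% | 0.7 | 0.601 | 0.681 | 0.667 | 8.0 |
| 70 | 50% | 0.85 | 0.827 | 0.848 | 0.843 | 2.1 |

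With no treatment effect, rejection rates were 0.043 to 0.053 for the planned test, 0.039 to 0.053 for rank ANCOVA and 0.039 to 0.060 for the stratified test. The Monte Carlo standard error at 0.05 is √(0.05 × 0.95/1500) ≈ 0.006, so all three are compatible with 5%.

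Extending the nil share to 60% in both cohort sizes gave rank ANCOVA the higher power in every setting, by about 1 to 16 points.

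**The case against.** The strongest reply is that nothing here is wrong. The planned test is prespecified, suited to an ordinal outcome and holds its type I error. The outcome is secondary with no power claim, so no design statement fails. That stands, and it limits the point to an efficiency improvement.

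Three stronger readings are tempting, and the protocol does not support them.
- A reader might infer that baseline is ignored. It is not: the outcome is change from baseline. Only use as a covariate or stratum is missing.
- A reader might infer that chance imbalance in baseline stereoacuity biases the comparison. Under randomization such imbalance is already within the nominal error rate. It costs precision, which is the same efficiency point again.
- A reader might infer that adjustment is free. The simple exact test stops being the lead analysis, and the question becomes 16-week level given baseline rather than change.

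It can also be said that the test fits the chapter. Fellow-eye loss of 2 or more lines, new or increased strabismus and diplopia are all compared with an unadjusted Fisher exact test, and 5.4.1 allows an unadjusted exact fallback. So the contrast is with the main visual acuity analyses only, not with every analysis. Those use a scale suited to ordinary ANCOVA, which stereoacuity may not be. A rank-based or stratified method answers that last point.

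Finally, the size of the gain rests on assumed inputs. That is so, and it is why a range is given. The direction was the same in every setting examined.

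**Conclusion.** The point holds as a minor efficiency improvement. Section 5.4.5 specifies a valid test that leaves part of the information in a routinely collected baseline unused. Under the stated assumptions a baseline-adjusted rank method gains roughly 1 to 16 points of power: about 12 to 14 points in the tabulated settings at correlation 0.5, and about 2 to 4 at 0.85. Type I error is near 5% either way.

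The size depends on the correlation, the number of levels and the nil share, none of which the protocol gives. It would be small if stereoacuity is highly reproducible over 16 weeks. The primary endpoint, the non-inferiority margin, the sample sizes and the primary conclusions are not affected.

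**What to change.** Amend Section 5.4.5 so that, within each cohort, the lead comparison is of 16-week stereoacuity by rank ANCOVA adjusting for baseline stereoacuity, or by a rank-sum test stratified by baseline stereoacuity level. Name one of the two. Keep the tabulation of change and the exact rank-sum test as supporting analyses. Settle this before any outcome data are examined, since it changes the lead test.

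The cost is a sentence or two of text and slightly more analysis work, with the exact test moved to a supporting role. No new data, visits or subjects are needed.

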5.4.6 Fellow-eye Contrast (Binocular computer treatment group)

Contrast of the fellow eye will be tabulated for the binocular computer treatment group based on automated iPad program logs at 4, 8, 12, and 16 weeks.

5.4.7 Safety

5.4.7.1 Visual Acuity in Fellow Eye

The mean change in fellow-eye visual acuity from baseline to 16 weeks will be calculated and compared between treatment groups using ANCOVA with adjustment for baseline visual acuity. The proportion of subjects with loss of 2 or more logMAR lines (10 or more letters) of visual acuity in the fellow eye from baseline to the 16-week exam will be reported for each treatment group and compared using the Fisher exact test.

5.4.7.2 Ocular Alignment

The proportion of subjects with development of new strabismus (no heterotropia at baseline and the presence of near and/or distance heterotropia at 16 weeks) or an increase from baseline $\geq 10\Delta$ in a pre-existing strabismus will be reported by treatment group and compared using the Fisher exact test.

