All subjects will be seen at 4, 8, 12, and 16 weeks after randomization. Subjects achieving amblyopic-eye visual acuity equal to or better than the fellow-eye visual acuity (0 or more lines better with ATS-HOTV, or 0 or more letters better with E-ETDRS) and at least 20/25 (or ≥ 78 letters if E-ETDRS) visual acuity in both eyes will be considered to have resolved and will discontinue treatment, although these subjects will still return for all remaining follow-up exams. If at a subsequent visit there is regression of amblyopia (≥ 2 logMAR lines or ≥ 10 letters from the best previous visual acuity), treatment will be restarted.

At each follow-up visit, we will assess distance visual acuity in each eye using ATS-HOTV for children <7 years at enrollment and the E-ETDRS for children ≥ 7 years at enrollment. We will also assess stereoacuity using the Randot Butterfly Stereoacuity test and Randot Preschool Stereoacuity test, history of diplopia, and ocular alignment by cover uncover test, simultaneous prism cover test (SPCT) (if deviation present), and prism and alternate cover test (PACT).

Analysis

The primary analysis in the younger cohort (ages 5 to < 13 year) will be a non-inferiority analysis of mean visual acuity change from enrollment at 16 weeks in the binocular computer treatment group compared with the patching group. The primary analysis in the older cohort (ages 13 to < 17 years) will be a superiority analysis of mean visual acuity change from enrollment at 16 weeks in the binocular treatment group compared with the patching group.

Study Summary Flow Chart

CHAPTER 2: SUBJECT ENROLLMENT

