If treatment precipitates the development of a manifest ocular deviation (e.g., esotropia) and/or diplopia, the parent will be advised to have the subject see the investigator as soon as possible. If a new manifest deviation is confirmed on examination, the decision as to whether to continue or discontinue therapy will be left to the investigator's and parent's decision. If the investigator determines that binocular diplopia is present, continuation of treatment is also at the discretion of the investigator and parent(s). If amblyopia treatment is to be discontinued during the study, a Protocol Chair should be called to discuss the case. Subjects discontinuing treatment during the study will continue to be seen for the remaining regularly scheduled study visits.

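### New strabismus and fellow-eye acuity loss are defined only by status at 16 weeks, so the stated safety comparison omits events that appear at an earlier visit and resolve

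*Protocol*

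**What the plan says.** Three parts of the Protocol bear on this.

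**Safety definitions.** Section 5.4.7.2 makes new strabismus depend on "no heterotropia at baseline and the presence of near and/or distance heterotropia at 16 weeks". Section 5.4.7.1 states that the proportion losing 2 or more lines of "visual acuity in the fellow eye from baseline to the 16-week exam will be reported for each treatment group". The companion summary is fixed in the same way: "The mean change in fellow-eye visual acuity from baseline to 16 weeks will be calculated and compared between treatment groups". Section 5.4.7 describes no analysis of either outcome at 4, 8 or 12 weeks.

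**Measurement.** Section 1.4 says "All subjects will be seen at 4, 8, 12, and 16 weeks after randomization". Section 3.5 introduces its list of tests with "The following procedures should be performed at each visit". The list includes alignment at distance and near, and for acuity "Monocular distance visual acuity testing will be performed in habitual refractive correction in each eye".

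**What happens after an event.** The risk text in section 4.6 (ahead of 4.6.2) considers a new manifest deviation brought on by treatment. Once it is confirmed, "the decision as to whether to continue or discontinue therapy will be left to the investigator's and parent's decision". A child who stops treatment stays in the visit schedule. Section 4.6.3 expects loss of fellow-eye acuity under patching to reverse in nearly all cases.

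**The concern.** A safety outcome read once, at the end, answers whether the child has the problem at 16 weeks. It does not answer whether the child developed it during treatment. The two differ when events can resolve, and the protocol describes ways in which they might. A child with a new deviation at week 4 who stops treatment and has no heterotropia at week 16 is event-free under section 5.4.7.2, although this is the harm that section 4.6 describes.

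Section 5.4.7 is the only between-arm safety analysis the Protocol states. Section 4.7 refers adverse events to local IRB requirements and mentions no pooled summary. The interim visits are used for other purposes: acuity over time (sections 1.2 and 5.4.2), compliance (5.4.4) and fellow-eye contrast (5.4.6). At stake is how completely the trial describes the risk of new strabismus and fellow-eye loss under a novel treatment. The primary efficacy result is not affected.

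**Working it through.** **Is there a figure to reproduce?** No. The Protocol gives no expected rate, power or sample size for these outcomes. The only planning figure borrowed below is 155 per group with outcome data in the younger cohort (section 5.2.1). It reproduces: 2 × (1.645 + 1.282)² × 0.15² / 0.05² = 154.2, rounded up to 155.

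**Measured against analysed**

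| Outcome | Measured at (weeks) | Visit named in 5.4.7 |
|---|---|---|
| New heterotropia | 4, 8, 12, 16 | 16 weeks |
| Fellow-eye loss of 2 or more lines | 4, 8, 12, 16 | 16 weeks |
| Mean fellow-eye change | 4, 8, 12, 16 | 16 weeks |
| Increase of 10 prism dioptres or more | 4, 8, 12, 16 | none |
| Diplopia | 4, 8, 12, 16 | none |

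The point is therefore exact for the first two rows, the event proportions. For the fourth, the text says only that an increase "in a pre-existing strabismus will be reported by treatment group and compared using the Fisher exact test".

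**Illustration of size (all rates assumed).** Let a share *c* of children have an event at some time, with onset equally likely in each of the four visit intervals. Let a fraction *r* of events with onset before the last interval be resolved by week 16. Then

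- seen at week 16 = c/4 + (3c/4)(1 − r) = c(1 − 0.75r)
- share missed = 0.75r

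| r | Share missed | Seen at week 16 if c = 8% | Children of 155 (12.4 ever) |
|---|---|---|---|
| 0.25 | 19% | 6.5% | 10.1 |
| 0.50 | 37.5% | 5.0% | 7.8 |
| 0.75 | 56% | 3.5% | 5.4 |

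**Effect on the comparison, same *r* in both arms.** Assume ever-event rates of 12% and 4% with 155 per group. Exact power of the two-sided Fisher test at 0.05 is 69% for ever-events. For 16-week status it is 57%, 42% and 27% at r = 0.25, 0.50 and 0.75. The ratio stays at 3, while the 8-point difference shrinks to 6.5, 5.0 and 3.5 points.

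**Effect on the comparison, different *r* by arm.** With the same 12% and 4%:

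- r = 0.75 in the 12% arm and 0.25 in the other: 12 × 0.4375 = 5.25% against 4 × 0.8125 = 3.25%, ratio 1.6.
- The reverse: 12 × 0.8125 = 9.75% against 4 × 0.4375 = 1.75%, ratio 5.6.
- Equal ever-rates of 8% with r = 0.25 and 0.75: 6.5% against 3.5%, a difference where there is none in ever-events.

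The direction depends on resolution rates by arm, which the documents do not give.

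**The case against.** The strongest defence is that status at a fixed time is a proper safety endpoint. Section 4.6.3 plays down fellow-eye loss because it reverses and has not been seen to last, which suggests that persistent loss is the harm of interest. For a child still on treatment, week 16 is also the point of greatest exposure. This stands as a reason to keep the 16-week result, but not as a reason to have no other.

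A second objection concerns measurement error. Section 2.5 itself says that microtropia is hard to diagnose. If a visit gives a false positive with an assumed probability of 2%, independently across visits, four visits give 1 − 0.98⁴ = 7.8%. A single 10-letter drop is open to the same problem. Children with more visits also have more chances to be counted. This stands too, and it argues against replacing the 16-week definition with an unconfirmed any-visit one.

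Third, a statistical analysis plan that is not shown may add by-visit safety tables, and the earlier data are collected in any case. The events are left out of the stated comparison, not lost. Even so, the 16-week time point is written into the definitions rather than left open.

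Some stronger readings are tempting but unsupported:

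- *All safety analyses are confined to 16 weeks.* The 10-prism-dioptre increase and diplopia name no visit.
- *The comparison is biased towards no harm.* That needs stopping or resolution rates by arm, and none are given.
- *A child who leaves early after an event is not counted at all.* Section 5.4.7 states no denominator or missing-data rule. Such a child has no 16-week status, but how the analysis would treat that is an inference.

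**Conclusion.** The point holds for two outcomes: new strabismus and fellow-eye loss of 2 or more lines. As written, the Protocol compares arms on 16-week prevalence and leaves out events that appear at 4, 8 or 12 weeks and resolve, although it measures them and foresees that they may resolve.

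The size is unknown. The range of 19% to 56% missed rests on assumed even onset over four intervals and on 25% to 75% of earlier events resolving. The power figures rest further on assumed rates of 12% and 4% and equal resolution in both arms. Neither the size nor the direction of any effect on the between-arm comparison can be derived from the documents. The 16-week definition is legitimate; the defect is that it is the only one. The diplopia definition is not part of this point.

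**What to change.** Keep the 16-week status in sections 5.4.7.1 and 5.4.7.2. Add, by treatment group and among children with at least one follow-up exam, the proportion with:

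- new heterotropia at any follow-up visit (4, 8, 12 or 16 weeks);
- fellow-eye loss of 2 or more lines at any follow-up visit.

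Beside each, show how many children had the event at more than one visit and how many still had it at 16 weeks. This separates repeated or persistent findings from isolated ones.

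The cost is a sentence in each section and a few table entries, with no new data, visits or procedures. The downside is that any-visit proportions carry more single-visit measurement error and depend on the number of visits attended. The number of visits attended by arm should be shown with them, and they should be read beside the 16-week row, not in its place.
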